13.2.2 Pilot Phase Interviews (to include exploration with Under-represented groups)

In addition, to the interviews described above, we will also explore under-representation within recruited participants, we will also aim to carry out the following:

During the pilot phase, we will carry out interviews (n = 5-10) with recruiting research team members to explore their attitudes, skills and confidence in recruiting women from underrepresented groups onto the trial. The sample will be taken to include diversity within recruiters including a sample of low/high recruiters.

 During the pilot phase and/or main trial, we will carry out interviews with trial participants and their carers/supporters (n = 5-10) to explore their experiences of participating in the trial. We will purposively sample for under-represented groups including older women, women from rural areas, those who are socio-economically disadvantaged and those from ethnic minority groups. The sample will be taken from the study database.

13.2.3 Informed Consent for PE Interviews

Contact details for patients and staff interview participants will be taken from the study database by study team e.g. Data Manager, Qualitative Researcher(s). Interview participants (patients and HCP/Trial Recruiters) will be sent (either by email or post according to their preference) an interview invitation with a PIS and ICF (either for patients or for HCP/Trial Recruiters). A study team member e.g. qualitative researcher(s)will also contact them by telephone or email to decide upon a date and time for the interview. For patient participants, HCPs/Trial Recruiters etc, the qualitative researcher will record oral consent.

Participants are free to withdraw from the research at any time. The withdrawal of consent will not affect data collection already carried out or the use of data collected prior to participant withdrawal. Participant data already collected prior to withdrawal will be retained according to the trial protocol.

13.2.4 Process Evaluation Data Protection

The qualitative researcher will record the interview on a password protected digital voice recorder or directly on to a CU approved platform e.g. Zoom Enterprise Version, Microsoft Teams or Skype for Business. When taking oral consent for HCPs/Trial Recruiters, consent will be recorded as a separate file to the interview. The interview will be transcribed verbatim and uploaded to a shared drive of the secure Cardiff University server as soon as possible. For all interview recordings, a study identification number will be used for the recording filename, which will not include any personal details such as participants' names. All files containing personal data will be password protected and stored in a folder with restricted access. After the recording has been successfully saved to the RDS Drive of the CU server and the recording has been checked, the data from electronic devices will be deleted permanently from digital recorders

Canolfan

Audio recordings will be securely sent to be transcribed verbatim (and anonymized) by an approved transcription company. Returned transcripts will be saved on the shared drive of the secure Cardiff University server. All files containing personal data will be password protected and stored in a folder with restricted access. Interview recordings will be transcribed using the Essential Secretary Smart Verbatim option. All interviews will be conducted remotely and captured via a Cardiff University approved platform (e.g. Zoom Enterprise Version, Microsoft Teams or Skype for Business) or a password protected digital recorder (and then transferred to the CU server)

Voice data and anonymised transcripts will be archived for at least 5 years after the project completion in line with Cardiff University policy. Participants can withdraw from the study and request that their data not be included in the analysis up until analysis is completed.

14 Pharmacovigilance

The Principal Investigator is responsible for ensuring that all site staff involved in this trial are familiar with the content of this section.

All SAEs must be reported immediately on a VESPER trial SAE form (and within 24 hours of knowledge of the event) by the PI at the participating site to the CTR PV and Safety Specialist unless the SAE is specified as not requiring immediate reporting (see section 16.2). This includes SAEs related to IMPs and non-Investigational Medicinal Products (nIMPs), noting however, that the VESPER trial does not have any nIMPs. Serious adverse events should be reported from time of signature of informed consent, throughout the treatment period up to, and including 7 days after the participant completes the trial protocol.

Definitions 14.1

Table 2 -Adverse event definitions

Term	Definition
Adverse Event (AE)	Any untoward medical occurrence in a participant or clinical trial participant administered a medicinal product and which are not necessarily caused by or related to that product

Adverse Reaction (AR)	Any untoward and unintended response in a clinical trial participant
	to an investigational medicinal product which is related to any dose
	administered to that participant
Serious Adverse Event	Any adverse event that -
(SAE)	Results in death
	 Is life-threatening*
	 Required hospitalisation or prolongation of existing
	hospitalisation**
	Results in persistent or significant disability or incapacity
	Consists of a congenital anomaly or birth defect
	 Other medically important condition***
Serious Adverse Reactions	Any SAE occurring in a clinical trial participant for which there is a
(SARs)	reasonable possibility that it is related to the IMP at any dose
	administered.
Suspected Unexpected	A SAR, the nature and severity of which is not consistent with the
Serious Adverse Reactions	Reference Safety Information (RSI) for the IMP.
(SUSARs)	

*Note: The term 'life-threatening' in the definition of serious refers to an event in which the trial participant was at risk of death at the time of the event or it is suspected that used or continued used of the product would result in the subjects death; it does not refer to an event which hypothetically might have caused death if it were more severe.

**** Note:** Hospitalisation is defined as an inpatient admission, regardless of the length of stay, even if the hospitalisation is a precautionary measure for continued observation. Pre-planned hospitalisation e.g. for pre-existing conditions which have not worsened, or elective procedures, does not constitute an SAE.

***** Note:** other events that may not result in death, are not life-threatening, or do not require hospitalisation, may be considered as an SAE when, based upon appropriate medical judgement, the event may jeopardise the participant and may require medical or surgical intervention to prevent one of the outcomes listed above.

14.2 Causality

Causal relationship will be assessed for IMPs and other trial treatments (medical device)::

Table 3 – Causality

IMPs:

Oral antibiotics as per NICE antimicrobial prescribing guidelines - Nitrofurantoin, Trimethoprim, Amoxicillin or Cefalexin.

Gentamicin (intravesical treatment)

Other Trial Treatment (Medical Device): Glycosaminoglycan (GAG) replacement compounds

(laluril, Cystistat, Gepan, etc)

The Principal Investigator (or another delegated medically qualified doctor from the trial team) and Chief Investigator (or another medically qualified doctor from the Trial Management Group) will assess each SAE to determine the causal relationship:

Relationship	Description	Reasonable possibility
		that the SAE may have
		been caused by the IMP?
Unrelated	There is no evidence of any causal relationship with the	No
	trial/intervention	
Unlikely	There is little evidence to suggest there is a causal	No
	relationship with the trial/intervention (e.g. the event	
	did not occur within a reasonable time after	
	administration of the trial medication). There is another	
	reasonable explanation for the event (e.g. the	
	participant's clinical condition, other concomitant	
	treatment).	
Possible	There is some evidence to suggest a causal relationship	Yes
	with the trial/intervention (e.g. because the event	

Table 4 -causal relationship

	occurs within a reasonable time after administration of	
	the trial medication). However, the influence of other	
	factors may have contributed to the event (e.g. the	
	participant's clinical condition, other concomitant	
	treatments).	
Probable	There is evidence to suggest a causal relationship and	Yes
	the influence of other factors is unlikely.	
Definite	There is clear evidence to suggest a causal relationship	Yes
	and other possible contributing factors can be ruled	
	out.	

The causality assessment given by the Principal Investigator (or delegate) cannot be downgraded by the Chief Investigator (or delegate), and in the case of disagreement both opinions will be provided.

14.3 Expectedness

The Chief Investigator (or another delegated appropriately qualified individual) will assess each serious adverse reaction to perform the assessment of expectedness.

The expectedness assessment should be made with reference to the current Reference Safety Information (RSI) for each IMP. Expectedness decisions must be based purely on whether the event is listed in the RSI; other factors such as the participant population and participant history should not be taken into account. Expectedness is not related to what is an anticipated event within a particular disease. SARs which add significant information on specificity or severity of a known, already documented adverse event constitute unexpected events. Fatal and life-threatening (LT) SARs should not be considered expected (unless explicitly stated in the RSI and approved by the NCA). For example, an event more specific or more severe than that described in the RSI is considered unexpected.

The table below lists the RSI's that should be referenced.

Table 5 - RSI Table

IMP	RSI to be used for	Relevant section to be used for
	expectedness assessment	expectedness assessment
Gentamicin (intravesical	SmPC for Gentamicin 1 mg/ml	Section 4.8 of SmPC
treatment)	solution for infusion	
Amoxicillin (Oral antibiotic)	SmPC for Amoxicillin 250 mg	Section 4.8 of SmPC
	Capsules	
Nitrofurantoin (Oral	SmPC for Nitrofurantoin 100	Section 4.8 of SmPC
antibiotic)	mg Capsules	
Trimethoprim (Oral antibiotic)	SmPC for Trimethoprim 50	Section 4.8 of SmPC
	mg/5 ml Suspension	
Cefalexin (Oral antibiotic)	SmPC for Cefalexin 125 mg/ 5	Section 4.8 of SmPC
	ml Oral Suspension	

Reference Safety Information (RSI) on any CTR trial will be reviewed regularly according to CTR procedures.

Intravesical treatments:

As the intravesical treatments are not absorbed systemically, the expected side-effects associated with the instillation process are listed below in **Error! Reference source not found.** :

Table 6: Expected events in relation to instillation of the intravesical treatments

Common	Less common	Rare
Mild bladder or urethral		
discomfort after		Blood in urine, severe
instillation	Urinary tract infection	pain after instillation

14.4 Reporting procedures

14.4.1 Participating Site Responsibilities

The PI (or delegated medically qualified doctor from the trial team) should sign and date the SAE form to acknowledge that he/she has performed the seriousness and causality assessments. Investigators should also report SAEs to their own health boards or trust in accordance with local practice.

A completed SAE form for all events requiring immediate reporting should be submitted via fax or email to the CTR within 24 hours of knowledge of the event. A separate form must be used to report each event, irrespective of whether or not the events had the same date of onset.

The participant will be identified only by trial number, date of birth or year of birth and initials. The participant's name (or any other personal identifiers) should not be used on any correspondence.

It is also required that sites respond to and clarify any queries raised on any reported SAEs and report any additional information as and when it becomes available through to the resolution of the event. Additionally, CTR/pharmaceutical companies may request additional information relating to any SAEs/SARs and the site should provide as much information as is available to them in order to resolve these queries.

Serious Adverse Event (SAE) email address:

[contact]

SAE [contact]

Serious adverse events and serious adverse reactions should be reported from time of signature of informed consent, throughout the treatment period up to, and including 7 days after the participant completes the trial protocol (ie 7 days after the 12-month follow up timepoint).

SAEs should be graded using the NCI Common Terminology Criteria for Adverse Events (CTCAE) Version 5.0

An SAE form should contain at least the minimum information:

- Full participant trial number
- An Adverse Event / Adverse Reaction

• IMP or trial intervention

• A completed assessment of the seriousness, and causality as performed by the PI (or another appropriately medically qualified doctor registered on the delegation log)

If any of these details are missing, the site will be contacted, and the information must be provided by the site to the CTR within 24 hours.

All other AE's will be captured on CRFs at the time of data collection at the scheduled follow-up appointments.

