	 Women willing to adhere to a 12-month study protocol 			
Exclusion criteria	Women (assigned female at birth unable to receive intravesical			
	treatments or second-line oral antibiotic prophylaxis			
	Women with structural or functional urinary tract abnormalities			
	considered contributory to rUTI			
	 Pregnancy or intended pregnancy in next 12 months 			
	• Fregulaticy of interfueu pregnaticy in flext 12 months			

	Women who are breast feeding			
	* If a patient has symptoms of a UTI at time of the eligibility assessment and a			
	subsequent urine culture test is positive, they will be treated for the UTI and			
	have a 4-week antibiotic wash-out period before being invited back to clinic to			
	complete eligibility, consent and randomisation.			
	The assessment of participants pregnancy status will be in line with current			
	clinical pathways, this involves asking the patient if there is any possibility of			
	pregnancy at the time of enrolment and follow-up during the trial. Proceeding			
	to pregnancy testing would only occur if the participant volunteers that there			
	may be a chance of pregnancy. If required, the pregnancy test used would be a			
	point-of-care urine test. As all of the treatments within the trial are in			
	widespread clinical use this approach mirrors existing clinical pathways albeit			
	within the context of this comparative clinical trial. Consequently, the routine			
	introduction of pregnancy testing for all participants is not advised.			
Treatment duration	6-months			
Follow-up duration	12-months post-randomisation (inclusive of 6-months treatment)			
Follow-up duration Planned trial period	12-months post-randomisation (inclusive of 6-months treatment)48 months			
Follow-up duration Planned trial period Primary objective	12-months post-randomisation (inclusive of 6-months treatment) 48 months . .			
Follow-up duration Planned trial period Primary objective	12-months post-randomisation (inclusive of 6-months treatment) 48 months 48 months . The primary objective is to evaluate the clinical and cost-effectiveness of two			
Follow-up duration Planned trial period Primary objective	12-months post-randomisation (inclusive of 6-months treatment) 48 months . The primary objective is to evaluate the clinical and cost-effectiveness of two experimental interventions for women with refractory rUTI: intravesical			

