9.6.2 Randomisation

Randomisation will be in a 1:3:3 ratio to receive: (1) Oral antibiotic prophylaxis (2) Intravesical Gentamicin (3) Intravesical GAG replacement for 6 months. To reduce the risk of imbalance of key covariates, the Pocock and Simon's minimisation method with an 80% random element will be used for previous UTI frequency (<=4/year; >4/year) and menopausal status (pre; peri/post) (see Section 15.1).

If a participant does not respond to their initially allocated prophylaxis or they experience intolerable side-effects, they can be re-randomised to one of the remaining two prophylactic regimes. Rerandomisation will be based on a 1:1 ratio. Re-randomisation will be based on block randomisation (see Section 15.1). If a participant does not respond to treatment following re-randomisation then they would be permitted to switch to the third treatment arm without the need for any further randomisation. If a participant is re-randomised to a different arm, their treatment will start back to time zero ie if a participant gets re-randomised at the end of their 6-months treatment period, they would be on the new treatment for a further 6-months.

Computerised web-based remote randomisation (available 24 hours a day) will be used. The randomisation system will be built by the in-house CTR information Systems and Technology Solutions team (TMS2). The CTR Trial team will also be notified that a participant has been randomised or rerandomised via an automated e-mail alert mechanism to the VESPER email inbox.

In the event that the online randomisation system is unavailable at site, or the site has problems accessing the online website, then the local investigator may contact the CTR (during office hours). Manual randomisation may be performed by CTR staff on request of the local investigator.

If the online system does not work, a telephone back-up managed by the CTR Trial team will be available for use during office hours Monday to Friday: 08:30-16:00.

For online randomisation: A randomisation/re-randomisation form must be completed on the trial database to randomise the participant.

For telephone randomisation: A randomisation/re-randomisation form must be completed before telephoning the randomisation line.

10 Withdrawal & lost to follow-up

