14.4.2 The CTR responsibilities

Following the initial report, all SAEs should be followed up to resolution wherever possible, and further information may be requested by the CTR. Follow up information must be provided on a new SAE form.

The CTR should continue reporting SAEs until 7days after the participant completes the trial protocol. Serious adverse reactions should continue to be reported until the end of follow up.

Once an SAE is received at the CTR, it will be evaluated by staff at the CTR and sent to the Chief Investigator (or their delegate) for an assessment of expectedness.

Investigator reports of suspected SARs will be reviewed immediately and those that are identified as SUSARs are reported to the MHRA, Main Ethics Committee.

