14.8.1 Contraception

The oral antibiotic Trimethoprim, used in this trial has a demonstrated or suspected human teratogenicity/fetotoxicity. The oral antibiotic Nitrofurantoin, used in this trial has demonstrated a risk of neonatal haemolysis when used in late pregnancy. The oral antibiotic Cefalexin is considered safe to use in pregnancy. Intravesical treatments are generally avoided during pregnancy due to the need for repeated bladder catheterisation. WOCBP entering into this trial must agree to use a highly effective method of contraception preferably with low user dependency for at least one month after the last dose of the trial treatment. A highly effective method of contraception is considered as having a failure rate of less than 1% per. Some acceptable contraception methods are listed below;

 combined (oestrogen and progestogen containing) hormonal contraception associated with inhibition of ovulation:

VESPER

- \circ oral
- o intravaginal
- o transdermal
- progestogen-only hormonal contraception associated with inhibition of ovulation
 - o oral
 - o injectable
 - implantable*
- intrauterine device (IUD)*
- intrauterine hormone-releasing system (IUS)*
- bilateral tubal occlusion*
- vasectomised partner*
- sexual abstinence defined as refraining from heterosexual intercourse during the entire period of risk associated with the trial treatments.

N.B. periodic abstinence (calendar, symptothermal, post-ovulation methods), withdrawal (coitus interruptus), spermicides only, and lactational amenorrhoea method (LAM) are not acceptable methods of contraception.

*These contraception methods are considered to be low user dependency.

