14.8.2 Pregnancy reporting whilst participating in the trial

Pregnancy, or the pregnancy of a partner occurring whilst participating in the trial, is not considered an SAE, however, a congenital anomaly or birth defect is. Other cases (e.g. termination of pregnancy without information on congenital malformation, and reports of pregnancy exposure without outcome data) should not normally be reported as such. When pregnancy occurs in a trial, either in a female participant or the female partner of a male participant, this should be followed up until at least the end of pregnancy, whether that is a live birth, termination of pregnancy etc. Without follow-up

of the pregnancy, it would not be possible for the CTR to know if a congenital anomaly or birth defect occurred, and therefore if there was an SAE that must be included in the safety evaluation of the IMP.

Information on a pregnancy in a VESPER trial participant will be captured by sites on the CTR Pregnancy Report Form (PRF) supplied to sites by the CTR. The PRF should be completed by the trial site within 7 days of becoming aware of the pregnancy and then emailed to the CTR ([contact]). Any participant identified as being pregnant whilst on the trial will, under the supervision of the principal investigator at site, have their trial treatment stopped. The site, on becoming aware of the pregnancy, will also complete a withdrawal form. The participant can choose to continue to provide follow-up data and or provide samples even though their trial treatment will be stopped.

VESPER sites must report pregnancy occurring within SAE reporting periods as stipulated in the trial protocol (from time of signature of informed consent, throughout the treatment period up to, and including 7 days after the participant completes the trial protocol). Congenital anomalies or birth defects are considered an SAE and so these events must also be reported to the CTR on a trial-specific SAE form. Congenital anomalies or birth defects related to the IMP and unexpected with respect to the IMP Reference Safety Information (RSI) must be submitted by the CTR within expedited SUSAR time frames (7 or 15 days) to the MHRA, relevant REC.

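### Safety and pregnancy reporting closes 7 days after month 12, but a woman re-randomised at month 6 can still be inside the protocol's own one-month post-dose contraception period

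*Protocol*

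**What the plan says.** **When reporting ends.** The introduction to section 14 runs serious adverse event (SAE) reporting "throughout the treatment period up to, and including 7 days after the participant completes the trial protocol". Section 14.4.1 applies this to SAEs and serious adverse reactions (SARs) and gives it a date: "up to, and including 7 days after the participant completes the trial protocol (ie 7 days after the 12-month follow up timepoint". Section 14.4.2 repeats the 7-day rule for SAEs but says of SARs: "Serious adverse reactions should continue to be reported until the end of follow up". For pregnancy, section 14.8.2 states: "VESPER sites must report pregnancy occurring within SAE reporting periods as stipulated in the trial protocol".

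**How long treatment can run.** Section 6 fixes the trial period at 12 months from randomisation for every woman. The synopsis gives follow-up as "12-months post-randomisation (inclusive of 6-months treatment". Sections 6 and 9.6.2 set the treatment clock back to zero at re-randomisation. Their example is a woman re-randomised at the end of her first 6 months: "they would be on the new treatment for a further 6-months". If that second treatment also fails, section 9.6.2 says she is "permitted to switch to the third treatment arm without the need for any further randomisation". It gives neither a latest date nor a course length for that switch.

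**The post-dose period.** Section 14.8.1 requires women of childbearing potential to use highly effective contraception "for at least one month after the last dose of the trial treatment".

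No section extends SAE, SAR or pregnancy reporting for women who are re-randomised or switched.

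**The concern.** The reporting window suits a woman who takes one 6-month course: her last dose and the month after it lie far inside it. Re-randomisation can move the last dose to month 12 or beyond, while the window stays tied to month 12. The end of the contraception month can then fall after reporting has closed.

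At stake is the capture of pregnancies and serious events in women who have had two or three regimens. Section 14.8.1 describes trimethoprim as a demonstrated or suspected teratogen. Section 14.8.2 explains that, unless a pregnancy is followed up, the trials unit cannot know whether a congenital anomaly, itself an SAE, has occurred. A pregnancy starting in the uncovered days would fall under no reporting duty in the protocol.

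Separately, the two different end points for SARs leave sites and the trials unit without one rule.

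**Working it through.** **Inputs.** Reporting close: 12 months + 7 days (14.4.1). Restarted course: 6 months (6, 9.6.2). Post-dose period: 1 month, the stated minimum (14.8.1). The 6-month and 12-month visits may each be up to 4 weeks late (13.1.3). I take 1 month = 365/12 = 30.4 days and round results to whole days.

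**Formulas.** Close = 365 + 7 = day 372. Last dose = day of re-randomisation + any start lag + length of dosing. End of post-dose period = last dose + 30.4. Gap = that day − 372; a negative value means covered.

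**The protocol's own example.** Re-randomised at month 6 (day 182.5) with 6 months of daily dosing: last dose = 182.5 + 182.5 = day 365, which is 7 days before the close. Post-dose period ends 365 + 30.4 = day 395. Gap = 395 − 372 = 23 days.

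**Other cases**

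| Case | Last dose (day) | Last dose minus close | End of post-dose month (day) | That end minus close |
|---|---|---|---|---|
| Never re-randomised | 182.5 | −190 | 213 | −159 |
| Re-randomised at month 3 | 274 | −98 | 304 | −68 |
| Re-randomised at month 6 | 365 | −7 | 395 | +23 |
| Month 6, first dose 14 days later (assumed lag) | 379 | +7 | 409 | +37 |
| Re-randomised at 6 months + 4 weeks (day 210.5) | 393 | +21 | 423 | +51 |
| Third-arm switch at month 7 (6-month course assumed) | 395 | +23 | 426 | +54 |
| Third-arm switch at month 9 (6-month course assumed) | 456 | +84 | 487 | +115 |

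**Break-even.** The close is at 372/30.4 = 12.23 months. With daily dosing, part of the post-dose month is uncovered when t + 6 + 1 > 12.23, that is, for re-randomisation after about month 5.23. Treatment itself passes the close when t plus any start lag exceeds about 6.23 months, for example a lag of more than 7 days after month 6.

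**Instillations.** The schedule gives 4 + 4 + 3 = 11, matching section 11.4. If the last falls 5 months after a restart at month 6, it is at month 11 and the post-dose month ends on day 365, 7 days before the close: no gap. If it falls at 6 months, the gap is 23 days as for daily dosing. With a restart at 6 months + 4 weeks, even the 5-month reading gives 210.5 + 152.1 + 30.4 = day 393, 21 days after the close.

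**Alternative anchor.** If the close is counted from an actual 12-month visit held 4 weeks late, it moves to 365 + 28 + 7 = day 400. The month-6 example is then covered (395 − 400 = −5). In the 6-months-plus-4-weeks case treatment ends 7 days before the close, and 423 − 400 = 23 days of the post-dose month remain uncovered.

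**SAR end date.** Section 14.4.1 gives day 372. Section 14.4.2 gives the end of follow-up, without a date. Taken as 12 months (synopsis), that is day 365, 7 days earlier than 14.4.1. Taken as the 13-month follow-up in section 13.1.3, it is about day 395, or up to 395 + 14 = day 409 with that visit's 2-week window. Neither equals day 372.

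**The case against.** The strongest reply is that little is left once assumptions are removed. Several parts of it stand.

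- **Still on treatment at the close.** A reader might infer that the month-6 example leaves a woman on treatment after reporting ends. It does not: her course ends 7 days before. The 4 weeks are a visit window, and nothing ties re-randomisation to that visit. Equally, nothing excludes re-randomisation there, a start lag or a late third-arm switch.
- **A third course to month 15.** The restart rule is written for re-randomisation, and the third-arm switch has no stated length. Six months is an assumption.
- **Reactions closing before unrelated events.** This is only one reading of section 14.4.2. Section 13.1.3 lists a 13-month follow-up, and on that reading SARs run longer than SAEs. What stands is the disagreement.
- **Exposed pregnancies never followed up.** This goes too far. A pregnancy inside the window is followed at least to its end (14.8.2), and in the month-6 example a conception on treatment falls inside it. Intended pregnancy is excluded and effective contraception required. The teratogenicity warning concerns trimethoprim, one of four named oral agents, and section 14.3 describes the intravesical treatments as not absorbed systemically.
- **Treatment sequences made to look safer.** No planned analysis supports this. Table 7 has adverse events summarised descriptively at 6 and 12 months, and the exploratory sequence objective concerns UTI rate.

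One defence fails. The reference to the treatment period in the reporting rule might seem to carry reporting along with a longer course, but section 14.4.1 spells the end point out as 7 days after the 12-month timepoint.

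**Conclusion.** The point holds in a limited form. In the protocol's own month-6 example, with daily dosing and nominal dates, about 23 days of the stated post-dose contraception month fall after SAE, SAR and pregnancy reporting has closed. This assumes that the post-dose month applies to re-randomised treatment, that the one-month minimum is used, and that the close is counted from the nominal 12-month date. Coverage should not depend on a visit happening to be late.

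A gap of about 21 days on treatment and 51 days in total needs re-randomisation at a 6-month visit held 4 weeks late. Anything longer needs a start lag or an assumed third-course length. The protocol does not allow the number of women affected to be derived: they are the late re-randomised or switched, and for pregnancy only those of childbearing potential.

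The SAR contradiction between sections 14.4.1 and 14.4.2 exists whichever reading of follow-up is taken. Both matters concern safety capture and leave the sample size and primary analysis untouched.

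**What to change.** Reconcile the introduction to section 14 and sections 14.4.1, 14.4.2, 14.8.1 and 14.8.2 with sections 6 and 9.6.2:

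1. End SAE, SAR and pregnancy reporting at the later of (a) 7 days after the 12-month follow-up and (b) the end of the protocol's own post-dose period after the last dose of any trial-allocated treatment, including treatment after re-randomisation or a third-arm switch.
2. State whether (a) counts from the nominal date or from the actual visit.
3. Give SARs one dated end point, the same in 14.4.1 and 14.4.2 and no earlier than that for SAEs.
4. Use the month-13 contact, already planned for all participants for the choice experiment, to ask about SAEs, pregnancy and the date of last dose.

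This changes no treatment or contraception rule. The cost is protocol wording and three questions at an existing contact. Month 13 falls at about day 395, which matches the end of the period in the month-6 example. For the few women whose period ends later, the site keeps reporting open somewhat longer.
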